## 7.2 Statistical Methods

### 7.2.1 Data Collection and Variables: (Table 2)

Study investigators/RAs will enter data directly into NYUMC-internal REDCap for use on iPad portable tablet computers.

Feasibility: The PI/RA will collect process data, including barriers and facilitators encountered in the completion of all study procedures, including data and reason for non-inclusion for all subjects approached but not enrolled.

Clinical Assessments: We will also extract data from assessments completed by clinical staff, which will include Medical Management and XT-NTX administration progress notes, Adverse Event Forms, and laboratory data (liver enzymes (AST, ALT, GGT), pregnancy, urine drug screen), which is consistent with prior and ongoing XR-NTX studies at our institution (PI: [name]).

Research Assessments (Aim 2): We will collect demographic information and assess a broad range of subject characteristics using validated, reliable questionnaires and other instruments that are widely-used, including in ongoing XR-NTX studies, and for which trainings are available. Data collection at enrollment and months 3, 6, and 12 will include several outcome variables of interest that we have broadly classified as drinking metrics, healthcare utilization, and quality of life. The 30-day Timeline Follow-Back (TLFB) for heavy drinking days is the standard method for assessing self-reported alcohol consumption. The Economic Form 90 notably was used in the COMBINE study and is currently in use by in ongoing alcohol research for assessment of a broad range of health and public sector services utilization (including medical, self-help, legal services) and cost-effectiveness analyses. The Short Index of Problems Related to Alcohol (SIP-2R), and EuroQol-5D (EQ-5D) will be used for quality of life assessments. We will also conduct a 30-minute semi-structured qualitative interview and assess craving (Penn Alcohol Craving Scale), Self-Efficacy (Alcohol Abstinence Self-Efficacy Scale (AASE)), and Patient Motivation and Satisfaction scales. We will collect blood levels of carbohydrate deficient transferrin and GGT, which are biomarkers used together to objectively quantitate heavy drinking. We will ascertain healthcare utilization by triangulating data from Bellevue/HHC hospitals databases, EMS ambulance transports to all NYC EDs, Medicaid claims data, and subject self-report.

Attachment #2 contains the full instruments from which selected questions and measures have been taken. Additional instruments are included that will serve as “back-up” instruments to replace measures that cannot be reliably completed by subjects (i.e. ongoing feasibility testing). Of note, we have included assessments and measures used by other investigator’s studying XR-NTX for alcohol dependence so that we may perform similar analyses and draw comparisons through potential future collaboration. These investigators (potential future collaborators) specifically include Drs. [name] at NYU and [name] at University of Washington (R01AA020836; R01 AA022309). To clarify, we will not use data from their studies nor share any identifiable data with these investigators, but rather perform analyses similar to those employed in their investigations.

CONFIDENTIAL

This material is the property of the NYU School of Medicine and Langone Medical Center. Do not disclose or use except as authorized in writing by the study sponsor

## 7.2.2 Statistical Analysis Plan

### **Aim 1: Feasibility and Acceptability:**

Formal statistical analysis is not planned for this primary aim, in which we will a) further develop and pilot procedures and b) descriptively document feasibility and acceptability of XR-NTX for frequent ED users with severe AUDs. Process data collected will be used to determine optimal processes for enrollment, medication administration, navigation to ambulatory care, and conducting assessments. Proportions will be generated for potential subjects who (1) are able and willing to consent; (2) accept injections, (4) attend clinic appointments, (5) complete planned 3-, 6-, and 12-month assessments. Subjects' acceptability will be assessed via interviews and questionnaires. We will extract qualitative themes from interview transcripts to inform the further development of intervention and improve acceptability.

**Safety Monitoring:** We will repeat laboratory analyses as specified and maintain an adverse-effect profile and drug accountability log. We will use vital statistics to track mortality in the event of drop-out.

### **Aim 2: Analysis of Effect:**

- a. We will explore the relative efficacy of XR-NTX+CM to standard care on decreasing acute healthcare use (ED, inpatient, other (ambulance, detoxification)) and associated expenditures.
- b. Secondarily, we will explore effects on healthcare engagement (clinic use, medication adherence, self-efficacy, motivation to change), alcohol quantity/frequency, alcohol-related consequences, quality of life measures, and cost-effectiveness.
- c. We will triangulate data sources for outcome measures to explore their correlation and to address missing data. Of specific interest, we will assess the performance of biomarkers (CDT and GGT, combinations) as an objective measure of changes in heavy drinking, which will inform the design of the second phase of study (definitive trial).

Although randomization would predict equal distribution of cofounders, we will examine their distribution and adjust accordingly. Interactions or confounding may occur between outcome domains (e.g. quality of life may have an effect on healthcare utilization); other cofounders may include age, race, sex, socioeconomic status, comorbidities, and social stability. See Figure 3.

We will ascertain healthcare utilization by triangulating data from subject self-report (Form 90) and from various other sources (pending availability), including Bellevue Hospital and New York City Health and Hospitals Corporation databases, partnering hospital medical records, EMS database of ambulance transports to all NYC EDs, and Medicaid claims data. We will report expenditures as reimbursement payments and/or using Medicaid payment rates as a cost proxy.

[figure not shown]
We will use a mixed-methods approach with questionnaires and instruments (See 7.2.1) that are widely-used as well as database analyses to assess heavy drinking days and other substance use (TLFB, Form 90), craving (Penn Alcohol Craving Scale), self-efficacy (AASE), and quality of life (EQ-5D), consequences related to drinking (SIP-2R, Form 90), health and psychosocial status and utilization of services (Form 90). Changes in heavy drinking will also be assessed (secondarily) via analysis of biomarkers (CDT and GGT combinations will be tested); described below in Aim 2c (below). Multiple endpoint variables will not be normally distributed. We will generate descriptive statistics to characterize subjects, describe the distribution of baseline health and functioning, and calculate changes in severity scores. We will adopt a mixed methods approach to identify relationships between these variables. We will use independent t-tests or Wilcoxon rank-sum tests to compare pre-treatment variables of the two groups, and paired t-tests or Wilcoxon signed-rank tests to test pre- to post-treatment changes within each group. We will conduct an intention-to-treat analysis of healthcare use and expenditures for the 6- and 12-month periods before and after intervention using differences-in-differences multivariate linear regression modeling and repeated measures analysis. Correlations between the triangulated outcome measures will be assessed and inform the second phase of study.

Short-term estimates of costs and effectiveness will be obtained using a combination of pre-specified medical record and survey endpoints using methods described by [name] in his protocol # S12-

CONFIDENTIAL

This material is the property of the NYU School of Medicine and Langone Medical Center. Do not disclose or use except as authorized in writing by the study sponsor

02263. Cost assessment will be conceptually similar to recently published analyses of the COMBINE interventions and will include medical and non-medical costs as well as payer and societal costs (Form 90). Effectiveness assessment will include alcohol consumption measures, quality of life, consequences, and the EQ-5D. The EQ-5D is among the most commonly used quality-of-life measure for informing cost-effectiveness analyses because it has minimal respondent burden, is well validated, and it yields utilities (preference-based measures on a scale of 0 to 1), the desired input for cost-effectiveness models. Because costs are skewed, incremental costs will be assessed using ordinary least squares and median regression models with covariates for treatment intervention and other relevant factors, and conditional models may be used because of cost data that may include “zeros.”

**Figure 3: The Predictor variables (study arms) are shown on the left and four outcome domains on the right (Healthcare utilization, Drinking, Quality of Life, and Consequences) with the specific measures noted alongside each domain. The outcomes may be mediated by the subjects' development of engagement (assessed by AASE scale, motivation visual analogue scale, adherence to treatment arm, and participation in clinic). Several potential interactions are hypothesized, some of which may also act as confounders. Interactions or confounding may occur between outcome domains (e.g. quality of life may have an effect on healthcare utilization); other cofounders may include age, race, sex, socioeconomic status, comorbidities, and social stability. Randomization will be employed to help mitigate potential threats.**

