**Study Personnel:** The PI will be responsible for all aspects of the study. The study investigators (PI, Co-Investigators, and RAs) will collect process data, including barriers and facilitators encountered in the completion of all study procedures. The PI and RA will conduct study procedures related to screening, the enrollment visit (week 0), and the research visits at weeks 12, 24, and 48. Biologic samples (blood/urine) will be collected by the PI, study clinicians, or clinical staff on duty. Providers administering XR-NTX may include physicians, physician assistants, and registered nurses. Medical Management and subsequent XR-NTX injections will be performed by trained Bellevue ambulatory care or ED providers. Care Management will be facilitated by Bellevue staff and/or community support staff.

**Subject Compensation:** Subjects will be compensated \$40 at enrollment and upon completion of research visits at months 3, 6, and 12. Subjects in both arms will also be compensated \$10 after the first (week 1) medical management visit. Subjects in the intervention arm will receive \$25 for each XR-NTX injection/clinical visit. In the event that the subject has a research visit and injection visit on the same day, the subject will only be compensated for the research visit. Certain costs associated with arranging transportation of subjects, study personnel, and/or other staff will be reimbursed for paid by covered by the study when necessary. Subjects will also receive food and small gifts in an effort to build trust.

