### Both Arms, Clinical Visit - Medical Management (MM) Visit (Ambulatory Care or ED)

- Subjects in both arms will be referred to Bellevue ambulatory care as scheduled for an initial visit for Alcohol-Medical Management (MM) to assess and manage adverse events, treatment effects, and support the goals of reducing the harms associated with alcohol use.
- Data will be extracted from the clinical note, including adverse events or concerns.
- Subjects in intervention arm who miss appointment will be contacted through methods described in Section 4.4.2. Follow up will be performed in the ED if subject cannot be navigated to ambulatory care. Subjects will be given a week 4 appointment.
- Subjects in the Standard Care Arm have no further clinical intervention beyond the initial referral but will have research assessments at weeks 12, 24, and 48. Any ongoing medical care will be left to the discretion of their (non-study) treating providers.

CONFIDENTIAL

This material is the property of the NYU School of Medicine and Langone Medical Center. Do not disclose or use except as authorized in writing by the study sponsor

### 6.3 Visit 3: Week 4

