## 7.3 Subject Population(s) for Analysis

For both the primary and secondary aims/outcomes, we will study an all-randomized population: Any subject randomized into the study, regardless of whether they received study drug.

We will also collect process data, including barriers and facilitators encountered in the completion of all study procedures. This data will include reason for non-inclusion for all subjects approached but not enrolled.

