### Cost to Subjects

Subjects will not incur any cost for the study medication. The drug manufacturer, Alkermes, Inc will provide the medication free of cost. Subjects and/or their insurance companies will be billed for medical management visits and associated laboratory tests per standard of care. Subjects will not be charged for biomarker or genetic testing.

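### Injection acceptance has no valid stated denominator, and clinic use is listed as an engagement effect although clinic visits after week 1 are scheduled, paid and chased only in the XR-NTX+CM arm

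*Combined protocol and SAP*

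**What the plan says.** Section 7.3 sets a single population for the primary and secondary aims: "we will study an all-randomized population: Any subject randomized into the study, regardless of whether they received study drug". No separate set is given for any measure.

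Section 7.2.2, Aim 1, uses a different group: "Proportions will be generated for potential subjects who (1) are able and willing to consent; (2) accept injections, (4) attend clinic appointments". The XR-NTX+CM arm is not named as the denominator for injections here or anywhere else.

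Section 7.2.2, Aim 2b, lists the engagement outcomes: "we will explore effects on healthcare engagement (clinic use, medication adherence, self-efficacy, motivation to change". Medication adherence is not defined, and clinic use does not separate protocol-scheduled visits from others. The Figure 3 legend gives engagement a further role: "The outcomes may be mediated by the subjects' development of engagement (assessed by AASE scale, motivation visual analogue scale, adherence to treatment arm", with participation in clinic also named.

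The arms differ in what they are offered. The Study Summary gives the reference as treatment as usual without medication. Section 6.2 refers both arms to a week-1 MM visit and then states: "Subjects in the Standard Care Arm have no further clinical intervention beyond the initial referral". Section 3.1 schedules MM-injection visits for the intervention arm at weeks 4 to 24, with possible further visits at weeks 28 to 44. Section 6 (Subject Compensation) pays both arms 10 dollars for week 1, and pays only the intervention arm 25 dollars "for each XR-NTX injection/clinical visit". Under Cost to Subjects (Section 15), subjects or their insurers "will be billed for medical management visits and associated laboratory tests per standard of care".

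**The concern.** Two measures are planned without regard to which arm can generate them.

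The first belongs to the primary aim. The share accepting injections is a main acceptability result of the pilot, and the pilot is meant to inform the definitive trial. Neither population in the text suits it. All randomised subjects include an arm never offered an injection. Potential subjects, taken literally, include people who never enrolled.

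The second is clinic use as an engagement outcome. One arm has a four-weekly clinic schedule, a payment per visit and active recontact after missed visits. The other has one scheduled clinic visit. More visits in the first arm would be expected even if the two groups were equally inclined to attend. Because MM visits are billed as ordinary care, they can enter the hospital and claims data from which utilisation is taken. The plan could then report as greater engagement something that its own schedule produced. For the study drug, adherence has no control-arm counterpart at all.

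**Working it through.** The plan gives no figure for injection acceptance, adherence or clinic use, so there is none to reproduce. The sample sizes in Section 7.1 do not enter.

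**Scheduled clinic visits** (Sections 3.1 and 6.2 to 6.13)
- XR-NTX+CM, core: weeks 1, 4, 8, 12, 16, 20, 24 = 7.
- XR-NTX+CM, extended: 7 + 5 (weeks 28, 32, 36, 40, 44) = 12.
- Standard care: week 1 = 1. Table 2 shows the week-24 clinical visit without an arm symbol, which would make this 2; Section 6.8 labels that visit intervention arm only.

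**Maximum scheduled payments** (Table 2; research and injection visits on the same day are paid once)
- Standard care: 4 × 40 + 10 = 170 dollars.
- XR-NTX+CM, core: 170 + 4 × 25 = 270 dollars.
- XR-NTX+CM, extended: 270 + 5 × 25 = 395 dollars.
- For clinic-only visits: 10 dollars against 10 + 4 × 25 = 110, or 110 + 5 × 25 = 235 if extended.

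**Clinic attendance with no difference in behaviour.** Let q be the probability of attending any scheduled visit, the same in both arms. Expected attended visits are 7q (or 12q) against q, a difference of 6q (or 11q). The protocol gives no q, so a range is assumed.

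| q | Standard care | Core | Extended | Difference, core | Difference, extended |
|---|---|---|---|---|---|
| 0.2 | 0.2 | 1.4 | 2.4 | 1.2 | 2.2 |
| 0.5 | 0.5 | 3.5 | 6.0 | 3.0 | 5.5 |
| 0.9 | 0.9 | 6.3 | 10.8 | 5.4 | 9.9 |

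If week 24 applies to both arms, the core difference is 7q − 2q = 5q, or 1.0 to 4.5 over the same range. A yes/no measure is affected too. At q = 0.3, with independent visits, the chance of at least one scheduled visit is 1 − 0.7^7 = 92% against 30%.

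**Injection acceptance.** Let p be the proportion accepting among those randomised to XR-NTX+CM. With all randomised subjects as denominator, 1:1 allocation and every control counted as a non-acceptor, the reported value is p × 1/(1 + 1) = p/2. Its ceiling is 25/50 = 50% in the pilot and 150/300 = 50% overall.

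- p = 90% would read 45%; 80% would read 40%; 60% would read 30%.
- Example: 20 acceptors of 25 is 80% (Wilson 95% interval 61% to 91%); 20 of 50 is 40%.

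Equal allocation is stated for phase 2 (125 per arm). For the pilot, 25 per arm is an assumption, suggested by the even block sizes.

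**The case against.** The strongest reply is that this is a gap in wording. Section 7.3 names an analysis population, not a pooled denominator for each proportion. Aim 1 cannot be using that population throughout, because its first item is willingness to consent. A reader might infer that the plan halves injection acceptance. The documents do not support that as fact: nothing tells the analyst to count controls as refusers. What stands is that the two sections conflict and neither names the arm that can accept an injection.

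A reader might also infer that the whole engagement effect is built in. That goes too far. Self-efficacy and motivation are assessed at research visits in both arms. Controls can attend clinics after their referral, and the intervention is a package that includes navigation to ambulatory care. A difference in total clinic use is thus a proper intention-to-treat effect of the package. It is the reading of that difference as engagement that fails.

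Nor does the plan contain a faulty mediation analysis. The Figure 3 legend says only that outcomes may be mediated, refers to adherence to treatment arm, and no mediation model is specified.

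Other reservations also stand. Undefined medication adherence could cover non-study drugs, since Section 5.6 allows concomitant therapy; the lack of a control counterpart is certain only for study drug. MM visits may take place in the ED, so not all would count as clinic use. The external data sources are subject to availability. The 395-dollar figure applies only to extended treatment. All of these analyses are descriptive or exploratory, but a descriptive proportion still needs a denominator.

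**Conclusion.** The point holds in limited form and should be acted on. Injection acceptance, a named proportion of the primary aim, has no valid stated denominator; halving is the size of the error under one reading and three conditions (pooled denominator, 1:1 allocation, controls counted as non-acceptors). Study-drug adherence is a process measure of one arm, not a between-arm effect. A difference in clinic use partly reflects 7 or 12 scheduled visits against 1 and the payments attached to them. At equal attendance per scheduled visit it would be 1.2 to 5.4 visits on the core schedule for attendance between 0.2 and 0.9, which is an assumed range. The visit and payment counts come from the documents; the attendance and acceptance rates are illustrations. Self-efficacy and motivation comparisons, the sample size and the power are not affected.

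**What to change.** 1. In Section 7.2.2, Aim 1, and Section 7.3, report injection acceptance and study-drug adherence descriptively among subjects randomised to XR-NTX+CM, as process measures and not as between-arm effects. Define medication adherence.
2. In Aim 2b, report total clinic use by arm as the intention-to-treat effect of the package. Beside it, show protocol-scheduled or paid MM/injection visits separately from other ambulatory visits, and do not interpret the scheduled component as engagement. Do not drop the scheduled visits from one arm only: MM follow-up that a control obtains through the same referral would still count, which would bias the comparison against the intervention.
3. Report completion of the 3-, 6- and 12-month assessments among all randomised subjects.
4. Reconcile Aim 1, Aim 2b, the Figure 3 legend and Section 7.3 on populations and on the role of engagement. Reconcile the week-24 clinical visit marking in Table 2 with Section 6.8.

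The cost is small: SAP wording, one visit-type flag and one extra breakdown. Visit notes and drug accountability records are already collected, and no trial procedure changes.

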project enrolling a total of 300 subjects in both phases. These estimates are founded in the current literature and the analyses, hypotheses, and predictions of experts in the field.

[name]'s ongoing study (R01AA020836) comparing the effectiveness of oral naltrexone to XR-NTX in alcohol dependent primary care patients has a targeted enrollment of n=117 in each of the two arms to detect a 20% absolute difference in primary clinical outcomes based in the Fisher's exact test with a projected power of 90%. [name], PhDs' (R01 AA022309) four-arm RCT of alcohol dependent homeless individuals recruited from a community housing program (XR-NTX + Counseling, Placebo + Counseling, Counseling alone, Treatment as Usual) will enroll a total of 300 patients (N=75/arm). This study population is similar to the one we will be studying.

A sample of 125 subjects per arm would allow us to detect a moderate effect size (Cohen's d of slightly less than 0.40) to provide power of 0.80 or greater at  $\alpha < .05$ . Another consideration when determining sample size is to power the study to detect the reduction in ED visits that would entirely offset the cost of medication. The institutional costs of a dose of Vivitrol (XR-NTX) is comparable to the estimated institutional cost of a single ED visit to Bellevue Hospital (according to the New York State Institute Cost Review). To detect a difference of  $\geq 6$  ED visits (i.e. a 6 month course of Vivitrol) between study arms comprised of subjects having a mean of  $22 \pm 15$  ED visits per year (per our pilot study data), would require 100 subjects per arm with  $\alpha = 0.05$ ;  $\beta = 0.20$  or, more conservatively, 133 subjects per arm with  $\alpha = 0.05$  and  $\beta = 0.10$ .

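### Aim 2 decides covariate adjustment after looking at balance between randomised arms, with no fixed covariate set and no limit to baseline values; always adjusting for each outcome's baseline value would be more precise at no cost

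*Combined protocol and SAP*

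**What the plan says.** Section 7.2.2, Aim 2, gives one rule for covariates: "Although randomization would predict equal distribution of cofounders, we will examine their distribution and adjust accordingly". The next sentence lists candidates in two groups. The first is other outcomes: "Interactions or confounding may occur between outcome domains (e.g. quality of life may have an effect on healthcare utilization". The second is subject characteristics: "other cofounders may include age, race, sex, socioeconomic status, comorbidities, and social stability". The Figure 3 caption repeats both groups and separately names a mediator: "The outcomes may be mediated by the subjects' development of engagement".

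A little further on, among the descriptive analyses, the plan adds: "We will use independent t-tests or Wilcoxon rank-sum tests to compare pre-treatment variables of the two groups". Healthcare use and expenditures are analysed by intention to treat "using differences-in-differences multivariate linear regression modeling and repeated measures analysis", with no covariates named. The cost models are regressions "with covariates for treatment intervention and other relevant factors", which are not listed. For drinking, quality of life and consequences, Aim 2 states paired within-group tests and names no between-arm model.

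Section 4.3.5 describes randomisation in permuted blocks of 2, 4 and 6 and names no stratification factor. Section 7.1 projects 125 subjects per arm for phase 2.

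**The concern.** In a properly randomised trial, any baseline difference between arms is chance. Looking at the difference says nothing about whether the variable predicts the outcome, and that is what decides whether adjusting for it helps. A rule triggered by imbalance therefore omits strong predictors that happen to be balanced and includes weak ones that happen not to be. The precision available from each outcome's own baseline value is used only by accident.

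Because the candidate list is open and no threshold or model is written down, the analysis model is also settled after the data can be seen.

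Finally, the text does not limit covariates to baseline values, yet it counts other outcome domains among the possible confounders. A follow-up value of such a domain may itself be changed by treatment, and nothing written keeps it out of an effect model.

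**Working it through.** **Inputs.** From Section 7.1: difference 6 ED visits, SD 15 (so d = 6/15 = 0.40), alpha 0.05, 125 per arm in phase 2. Sidedness is not stated for this calculation; two-sided is assumed. The documents give no correlation r between baseline and follow-up values, so a range is assumed.

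**1. The plan's own figures.** n per arm = 2(z₀.₉₇₅ + z_power)² × SD²/difference².
- 80% power: 2 × (1.960 + 0.842)² × 225/36 = 98.1, so 99. The t-based solution is 99.1, which rounds up to the stated 100.
- 90% power: 131.3, so 132. The t-based solution is 132.3, which rounds up to the stated 133.
- At 125 per arm: 6/(15 × √(2/125)) = 3.162, and power = Φ(3.162 − 1.960) = 0.885.

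The stated sample sizes reproduce. They are unadjusted two-sample figures.

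**2. Always adjusting, and the change score.** Adjusting for the baseline value replaces the SD by 15√(1 − r²). A simple change score replaces it by 15√(2(1 − r)), assuming equal SDs before and after. At r = 0.4 the adjusted SD is 13.75, giving 6/(13.75 × 0.1265) = 3.450 and power Φ(1.490) = 0.932. The change-score SD is 16.43, giving 2.887 and power Φ(0.927) = 0.823. Over the range, at 125 per arm:

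| r | Unadjusted | Change score | Always adjusted |
|---|---|---|---|
| 0.3 | 0.885 | 0.762 | 0.912 |
| 0.4 | 0.885 | 0.823 | 0.932 |
| 0.5 | 0.885 | 0.885 | 0.955 |
| 0.6 | 0.885 | 0.942 | 0.977 |
| 0.7 | 0.885 | 0.983 | 0.993 |

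**3. Adjusting only when imbalance is seen.** This was simulated at 125 per arm, adjusting only when the baseline test gives p < 0.05 (an assumed threshold, since the plan gives none). Power at d = 0.40 is about 0.88 to 0.90 for r from 0.4 to 0.7, close to no adjustment at all. Under no effect, rejection stays at about 3.5% to 5%.

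**4. Several covariates.** With six independent covariates, matching the number the plan names, simulated power for no adjustment, imbalance-triggered adjustment and adjustment for all six is 0.88, 0.90 and 0.97 if together they explain 36% of outcome variance. If they explain 10%, it is 0.88, 0.88 and 0.91.

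**5. How often chance imbalance would appear.** With six independent tests at 0.05, the probability of at least one significant difference under perfect randomisation is 1 − 0.95⁶ = 0.265.

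**The case against.** Four points can be made for the plan.

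- **No significance-test rule is written.** The adjustment sentence speaks only of examining distributions, and the baseline tests appear separately without being tied to covariate choice. This stands: selection by p-value is an inference from two neighbouring sentences. What is written is still a rule that depends on observed balance.
- **The main utilisation model already uses the pre-period value.** This also stands, for healthcare use and expenditures. At r = 0.7 the change score is only about 1 point behind full adjustment (0.983 against 0.993). Below r = 0.5 it is worse than no adjustment, and it is not stated for drinking, quality of life or consequences.
- **Aim 2 is exploratory at first.** True of phase 1. Phase 2 is meant to settle the effect, and no other Aim 2 model is given for it.
- **Aim 3 names baseline prognostic terms.** It does, for a logistic model of treatment success. They are not carried over to Aim 2.

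Two stronger readings are tempting. A reader might infer that the plan will adjust for follow-up quality of life and so remove part of the treatment effect. If treatment moved quality of life by 0.3 to 0.5 SD and that moved visits by 0.3 to 0.5 SD per SD (all assumed), the part removed would be 0.09 to 0.25 of the 0.40 SD effect. But no text says a post-randomisation value enters an effect model. The reference to what randomisation would balance points to baseline variables; quality of life is also measured at enrolment, where adjusting for it is harmless; and the Figure 3 caption treats mediation separately.

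A reader might also infer an inflated false-positive rate. Taking the best p-value over all 64 subsets of six covariates gives about 11% to 17% in simulation, but the plan describes no such search, and the imbalance rule alone does not inflate the error rate.

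**Conclusion.** The point holds as a free improvement in method. Aim 2 ties adjustment to observed balance, fixes no covariates and does not confine them to baseline values. The cost is forgone precision and a model left open until data are seen. Against always adjusting for the baseline value (93% to 99% power at 125 per arm and d = 0.40), imbalance-triggered adjustment gives about 88% to 90% and a simple change score 82% to 98%.

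These figures rest on an assumed r of 0.4 to 0.7, a two-sided 0.05 test, normal outcomes with equal SDs, and an imbalance threshold of p < 0.05 that the plan does not state. With weak covariates the gain is a few points at most. The stated sample sizes are not invalidated. Type I error inflation is not shown, and loss of treatment effect through a post-randomisation covariate is a risk the wording leaves open, not an analysis the plan states. The point matters most for phase 2.

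**What to change.** In Section 7.2.2, Aim 2, replace the adjustment sentence with a rule of this kind, applied at least to the phase 2 effect analysis:

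- Every between-arm model adjusts for the baseline value of its own outcome, plus a short list of baseline covariates fixed before outcome data are examined, whatever balance is observed. For healthcare use, the baseline value is the count in the matching pre-period.
- The list is for the sponsor to choose on prognostic grounds. Age, housing status and baseline heavy drinking days are natural candidates. Sex would probably add little, given 124 men among 129 patients in the dataset cited in Section 4.3.6.
- The same list replaces the unspecified factors in the cost models.
- Baseline comparisons between arms are presented descriptively, and no test is used to select covariates.
- Only baseline values enter the primary effect models. Relations between outcome domains, and engagement as a mediator, go to a separate mediation analysis labelled as such.

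The cost is a change of wording. The baseline outcome measures, demographics and psychosocial status are already collected at enrolment, so no visit, form or subject is added.
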